13. ADVERSE EVENT

13.1 General

National Cancer Institute/Common Terminology Criteria for Adverse Events (CTCAE) v4.0 will be the guideline for this study in describing, grading, and reporting of adverse events. Adverse events believed to be related to weight loss or metformin will be reported. Adverse event information will be collected during each in-person visit from screening phase onward. Only adverse events possibly, probably or definitely related to study interventions will be tabulated and reported according to NIH guideline (insert reference). All serious adverse events, regardless of relation to study interventions must be reported to the principle investigator. All adverse and serious adverse events will be reported to the local institutional review board. Any modification to consent and/or study protocol, resulting from an adverse event, will be provided to IRB with the report of the adverse event.

Definitions

- Adverse event (AE): Any undesirable sign, symptom, or medical condition occurring after starting therapy, even if the event is not considered to be related to the study. An undesirable medical condition can be symptoms (e.g., nausea, chest pain), signs (e.g., tachycardia), or abnormal results of a procedure (e.g., laboratory findings, biopsies).

Medical conditions/diseases present before starting study treatment are only considered adverse events if they worsen after starting study treatment and are believed to be related to the weight loss or metformin intervention.

- Serious adverse event or reaction: Any untoward medical occurrence secondary to therapy that: results in death, is immediately life-threatening, requires inpatient hospitalization or prolongation of existing hospitalization, results in persistent or significant disability, or is an important medical event that may jeopardize the subject or may require medical intervention to prevent one of the outcomes listed above.

The definition of a serious adverse event (experience) also includes an *important medical event*. Medical and scientific judgment should be exercised in deciding whether expedited reporting is appropriate in other situations, such as important medical events that may not be immediately life-threatening or result in death or hospitalization but may jeopardize the patient or may require intervention to prevent one of the other outcomes listed in the definition above. These should also usually be considered serious.

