A hospitalization planned before the start of the study agent(s) and/or for a preexisting condition that has not worsened does not constitute a serious adverse event (e.g., elective hospitalization for breast reconstruction). A hospitalization for a social reason in the absence of an adverse event also does not meet the criteria for a serious adverse event.

- Unexpected adverse event: An adverse event, which varies in nature, intensity or frequency from information on the investigational intervention provided in the Investigator's

Brochure, package insert, or safety reports. Any adverse event that is not included in the informed consent is considered “unexpected”.

- Expected (known) adverse event: An adverse event, which has been reported in the Investigator’s Brochure. An adverse event is considered “expected”, only if it is included in the informed consent document as a risk.

Relationship

An investigator will assess the relationship between adverse events to study intervention as follows:

- Definitely: An adverse event, which has a timely relationship to the administration of the investigational drug/agent, follows a known pattern of response, for which no alternative cause is present.
- Probably: An adverse event, which has a timely relationship to the administration of the investigational drug/agent, follows a known pattern of response, but for which a potential alternative cause may be present.
- Possibly: An adverse event, which has a timely relationship to the administration of the investigational drug/agent, follows no known pattern of response, but a potential alternative cause does not exist.
- Unlikely: An adverse event which does not have a timely relationship to the administration of the investigational drug/agent, follows no known pattern of response, does not reappear or worsen after re-administration of the investigational drug/agent (if applicable), and for which there is evidence that it is related to a cause other than the investigational drug/agent.
- Unrelated: An adverse event, for which there is evidence that it is definitely related to a cause other than the investigational drug/agent. In general, there is no timely relationship to the administration of the investigational drug/agent, or if there is a timely relationship, the event does not follow a known pattern of response, and there is an alternative cause.

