13.2 Potential Risk from Intervention

Side effects associated with weight loss, such as anxiety, may occur. Unlike with our intended lifestyle weight loss target (5% weight loss from baseline), a major weight loss may be associated with side effects including dehydration, electrolyte imbalance, malnutrition, nausea, tachycardia and headaches. Side effects from metformin include nausea, diarrhea, abdominal bloating, metallic taste, anorexia, or flatulence, vitamin B12 deficiency, and rarely, lactic acidosis. When blood samples are collected from participants, blood draw procedures may produce risk.

The followings are potential risk associated with the followings:

Potential risks associated with **Coach-Directed Behavioral Weight Loss** intervention and respective measures to minimize risk:

A- Nutrient Intake

Inadequate nutrition or excessive, rapid weight loss can result from calorie restriction. To minimize these risks, participants are encouraged to maintain adequate calorie level and eat a variety of foods from all food groups. Participants will be advised about serious health risks associated with sustained caloric restriction. Intervention can be suspended, and participant will be referred to the PCP if nutritional deficiency is suspected and participant is unresponsive to advice from study staff.

B- Hypoglycemia

Low blood glucose level can result from severe caloric restriction and exercise. To minimize this risk, participants will be educated about the signs and symptoms of low blood sugar, when to contact their PCP, and adequate calorie levels and the food groups to consume while under the lifestyle intervention. The study team will engage the PCP in this intervention arm.

C- Symptomatic Hypotension

For those who use anti-hypertensive medication, lifestyle medication interventions have the potential to increase the risk of hypotension. Participants are educated about symptoms of hypotension and urged to contact their PCP if they have symptoms suggestive of hypotension. Overall blood pressure management will be under the PCP responsibility.

D- Cardiovascular Events

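### The causality scale in section 13.1 refers to a drug that two of three arms do not receive, and Possibly is stricter on alternative causes than Probably, so events can drop out of the only adverse event table

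*Combined protocol and SAP*

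**What the plan says.** Everything here is in the combined protocol and SAP.

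- **What is to be rated.** Section 13.1, under Relationship, opens: "An investigator will assess the relationship between adverse events to study intervention as follows". Earlier in the same section: "Adverse events believed to be related to weight loss or metformin will be reported".
- **What the levels say.** Definitely, Probably and Possibly each require a timely relationship to administration of the investigational drug or agent. Definitely adds a known response pattern and no alternative cause. Probably adds a known pattern and tolerates a potential alternative cause. Possibly is defined by a "timely relationship to the administration of the investigational drug/agent, follows no known pattern of response, but a potential alternative cause does not exist". Unlikely requires that there is no timely relationship. Unrelated requires evidence that another cause is definitely responsible. Its second sentence, offered as what generally applies, also covers a timely event with no known pattern and an alternative cause. Unlikely and Unrelated both describe the other cause as one other than the drug or agent.
- **What the rating controls.** "Only adverse events possibly, probably or definitely related to study interventions will be tabulated and reported". Section 17 specifies no other adverse event table.
- **What coaching is expected to cause.** Section 13.2 lists inadequate nutrition, hypoglycemia, symptomatic hypotension and cardiovascular events as risks of the coach-directed arm. On hypotension it says that "lifestyle medication interventions have the potential to increase the risk of hypotension".
- **Serious events.** Section 13.1 defines a serious adverse event as "Any untoward medical occurrence secondary to therapy that: results in death" or meets one of the other listed outcomes. The same section says: "All serious adverse events, regardless of relation to study interventions must be reported to the principle investigator".

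**The concern.** A causality scale has to work in every arm, and its levels should run in order. This one raises doubts on both counts, and the rating decides what enters the safety table.

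If the reference point is a drug, a rater in the coach-directed or self-directed arm has no administration to time an event against. Raters must then improvise, and nothing ensures that they do so alike across arms. A comparison of related events between arms would partly reflect how the scale was stretched.

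If a weaker level is stricter on alternative causes than a stronger one, the events lost are the unfamiliar ones with an uncertain explanation. Those are the events that a category such as Possibly should keep in view.

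The serious event definition raises a related doubt. If an event counts as serious only when therapy caused it, the instruction to report serious events whatever their cause loses much of its force.

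**Working it through.** The plan gives no figure to reproduce here. The check sets the definitions side by side and asks where each kind of event lands.

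**1. Arms without a drug.** Sections 4 and 16 give 1:1:1 allocation of about 120 participants, so 120 / 3 = 40 per arm. Only the metformin arm receives a drug. The other two arms hold 2 × 40 = 80 of 120 participants.

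**2. Where events land.** Cross three criteria from the scale: timely (yes, no), known pattern (yes, no) and alternative cause (none, potential, definite). That gives 2 × 2 × 3 = 12 combinations. For an arm with a drug:

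| Timely | Known pattern | Alternative cause | Level | In the table? |
|---|---|---|---|---|
| Yes | Yes | None | Definitely | Yes |
| Yes | Yes | Potential | Probably | Yes |
| Yes | Yes | Definite | Unrelated | No |
| Yes | No | None | Possibly | Yes |
| Yes | No | Potential | No related level; described only by the second sentence of Unrelated | No |
| Yes | No | Definite | Unrelated | No |
| No | Either | Any | No related level (6 combinations) | No |

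The fifth row is the defect. The event fails Probably because it has no known pattern, fails Possibly because an alternative cause may exist, and fails Unlikely because it is timely. It does not meet the first sentence of Unrelated either, because a potential cause is not a definite one.

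Among timely events whose alternative cause is absent or only potential, there are 2 × 2 = 4 combinations. Three reach a related level and one does not.

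The untimely combinations are not part of the point. Three of the six fit no level strictly, but a scale that requires timing would not call any of them related.

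**3. Arms without a drug, read literally.** All three related levels need timing against drug administration. With no administration, no combination reaches a related level. That includes hypoglycemia or hypotension in the coach-directed arm, both of which section 13.2 anticipates.

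**4. Serious events.** The general adverse event definition in section 13.1 includes events not considered related to the study. The serious event definition adds that the occurrence is secondary to therapy. Taken at its word, an unrelated death or hospitalization is not a serious adverse event, so the rule to report serious events regardless of relation would not reach it.

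**The case against.** The strongest reply is that the drug wording is leftover template text and the intent is clear. The lead-in names the study intervention, section 13.1 covers events related to weight loss as well as metformin, and section 13.2 lists coaching risks. A sensible investigator would rate coach-arm events. This stands as far as it goes. A reader might infer that coaching will show no related events by definition, but that holds only if every rater ignores the lead-in. What remains is a conflict between the lead-in and the levels, and intent does not tell a rater what to time an event against.

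A reader might also infer that many metformin-arm events are lost. The documents do not support that. The listed metformin effects (gastrointestinal symptoms, vitamin B12 deficiency, lactic acidosis) can still be rated Probably when another cause is possible. Only timely, off-pattern events with a potential alternative cause are affected, and no rate is given for them. Their assignment to Unrelated is not certain either, since its first sentence asks for definite evidence and its second only states what generally applies.

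Other safety routes do not pass through the rating. Section 13.1 sends all adverse and serious adverse events to the IRB. Section 2 lists a side effects questionnaire as an outcome at 6 and 12 months. Section 9 collects a general symptoms form at follow-up visits, and section 14.3 provides for annual committee review. It would be wrong to conclude that safety oversight as a whole fails.

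On serious events, section 13.1 takes care to exclude planned and social hospitalizations, which would be largely needless if only therapy-caused events counted. That suggests the broad reading is meant, so it goes too far to say the reporting rule has nothing to act on. The two sentences still conflict as written.

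**Conclusion.** The point holds as a wording defect with a limited but real consequence, and it should be corrected.

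- The five levels do not match the stated object of the rating. About 80 of 120 participants have no drug for the levels to refer to. The practical result is discretion that may differ by arm.
- Possibly and Probably are out of order on alternative cause. One of the four timely combinations with no definite other cause is left without a related level.
- Because a related rating is the entry condition for the only adverse event table the plan states, affected events can be missing from it. The number cannot be computed from the documents.
- The serious event definition and the rule to report regardless of relation contradict each other.

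The conclusion rests on reading the definitions as written, and on sections 13 and 17 being the only places where adverse event tabulation is specified. The damage is to the trial's tabulated safety results and to the comparison of arms, not to every route of safety reporting.

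**What to change.** In section 13.1 and on the adverse event form:

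1. Replace every reference to the investigational drug or agent, at all five levels, with *the assigned study intervention*. This must include the phrases in Unlikely and Unrelated about a cause other than the drug. Otherwise an event definitely caused by coaching would still literally meet Unrelated.
2. Reword Possibly to: *timely relationship; follows no known pattern of response; a potential alternative cause may or may not be present*. The absence of a known pattern must stay a requirement, because making it one of two options would let Possibly overlap Probably. Limit the second sentence of Unrelated to a definite other cause. Each of the six timely combinations above then has one level.
3. Delete the condition that a serious adverse event be secondary to therapy.
4. Tabulate all collected adverse events by arm, with related events as a subset. This keeps events visible when ratings are uncertain. It does not replace items 1 and 2, since the related subset still depends on the scale.

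The cost is rewording in one section and on one form, plus one more table. No new data or visits are needed. Somewhat more events will be rated possibly related and will need reporting.

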13.2 Potential Risk from Intervention

Side effects associated with weight loss, such as anxiety, may occur. Unlike with our intended lifestyle weight loss target (5% weight loss from baseline), a major weight loss may be associated with side effects including dehydration, electrolyte imbalance, malnutrition, nausea, tachycardia and headaches. Side effects from metformin include nausea, diarrhea, abdominal bloating, metallic taste, anorexia, or flatulence, vitamin B12 deficiency, and rarely, lactic acidosis. When blood samples are collected from participants, blood draw procedures may produce risk.

The followings are potential risk associated with the followings:

Potential risks associated with **Coach-Directed Behavioral Weight Loss** intervention and respective measures to minimize risk:

A- Nutrient Intake

Inadequate nutrition or excessive, rapid weight loss can result from calorie restriction. To minimize these risks, participants are encouraged to maintain adequate calorie level and eat a variety of foods from all food groups. Participants will be advised about serious health risks associated with sustained caloric restriction. Intervention can be suspended, and participant will be referred to the PCP if nutritional deficiency is suspected and participant is unresponsive to advice from study staff.

B- Hypoglycemia

Low blood glucose level can result from severe caloric restriction and exercise. To minimize this risk, participants will be educated about the signs and symptoms of low blood sugar, when to contact their PCP, and adequate calorie levels and the food groups to consume while under the lifestyle intervention. The study team will engage the PCP in this intervention arm.

C- Symptomatic Hypotension

For those who use anti-hypertensive medication, lifestyle medication interventions have the potential to increase the risk of hypotension. Participants are educated about symptoms of hypotension and urged to contact their PCP if they have symptoms suggestive of hypotension. Overall blood pressure management will be under the PCP responsibility.

D- Cardiovascular Events

All participants with cardiovascular disease (CVD) require approval from their PCP prior to enrolling. PCPs are provided with information about safety guidelines for physical activity for people with CVD. In addition, participants are educated about CVD symptoms and urged to contact 911 in case of emergency or their PCP if they have a change in their CVD symptoms. In case a participant develop any CVD event, the intervention will be suspended until a decision to restart is authorized by the participant's PCP and the study principle investigator. Overall CVD management remains under the control of the participants PCP.

Potential risks associated with **Metformin** interventions and measures to minimize potential risks.

A- Gastrointestinal symptoms

B- Nausea, diarrhea, abdominal bloating, metallic taste, anorexia, and flatulence are associated with metformin use. If a participant develops mild symptoms that can be tolerated, then metformin will continue. If symptoms are difficult to tolerate, metformin will be stopped temporarily to establish association with the symptoms. Weekly or lessfrequent titration to maximum tolerated dose will be used to minimize

gastrointestinal symptoms. Restarting and continuation of metformin will be based on clinical judgment regarding severity of symptoms and tolerance of symptoms by participant.

C- Lactic Acidosis

Metformin is rarely associated with lactic acidosis (approximately 0.03 cases/1000 patient-years; no cases reported in 20,000 patient-years of exposure to metformin in clinical trials).⁸⁶ If a participant is hospitalized and develops metabolic acidosis, metformin will be stopped. Clinical judgment will guide the decision to restart metformin after resolution of acidosis based on understanding of the etiology of the cause of the acidosis. D- Anemia Vitamin B12 blood levels decrease to sub-normal levels without any clinical manifestations in approximately 7% of patients treated with metformin in clinical trials;⁸⁶ this is very rarely associated with anemia. However in long term high dose use, there may be a slightly lower hemoglobin level.⁶³ If anemia or vitamin deficiency is suspected, study physician will order vitamin B12 test.

E- Hypersensitivity to metformin

Participants who develop an allergic reaction or hypersensitivity to metformin will discontinue metformin.

F- Other adverse events

Interim events will be ascertained every three months, and serious adverse events will be reported per institutional review board and FDA regulations.

Safety Monitoring and Measures to Reduce Potential Drug-Related Side Effects

Standard laboratory studies will be done for each participant in the metformin arm. eGFR and complete blood count will be measured for eligibility. A complete blood count, and basic metabolic panel (including eGFR) will be measured at 12 months.

The most common side effects, reported by 28% of persons taking metformin, are gastrointestinal symptoms, among which nausea, diarrhea, abdominal bloating, metallic taste, anorexia, or flatulence are included.⁶³ These side effects are usually transient and resolve spontaneously or can be controlled by graduate dosing. Rarely, metformin can cause lactic acidosis among persons with renal or hepatic insufficiency, especially during episodes of hypoxia or circulatory failure. In addition, about 6-9% persons on metformin develop reduced vitamin B12 levels.⁸⁶

Potential risks associated with **blood** draw procedure and measures to minimize potential risks

A- Blood draw may produce discomfort, pain, bruises, and rarely, infection, syncope, or bleeding. Out trained staff will follow standard phlebotomy protocol for infection prevention and control, safety equipment and best practices.

13.3 Alert Levels

Laboratory studies and physical measurements will be obtained. For laboratory studies, we will use the alert values of the laboratory that performs the assays. For example, if the laboratory reports an alert level, study staff will be notified, and a clinician (either study nurse or physician) will contact the participant. Study physicians will also review and sign/initial each laboratory report, which we will then provide participants. ProHealth, a major clinical research unit for cardiovascular disease prevention studies, also has well established procedures and thresholds for other measurements such as blood pressure. If a participant's blood pressure is elevated, study staff will advise the participant to see their personal provider, using wellaccepted BP thresholds.

14. DATA AND SAFETY MONITORING

14.1 Data Management System

All information will be collected through the study website or using case-report forms. All studyrelated data will be reviewed for accuracy by the Project Manager or Database Manager. A periodic review will be done by the data analysis team.

14.2 Meetings

Regular meetings between the co-investigators and the study team will take place; additional meetings will be called as needed. Periodic meetings between the principal investigator, study coordinator, biostatistician, and data manager will take place to discuss study, progress, protocol adherence and objectives.

